3.3. SCP-111 Autoinjector

The SCP-111 Autoinjector is an investigational single-entity, drug-device combination product containing SCP-111 (furosemide injection), 80 mg/1 mL for subcutaneous use, prefilled in a 1 mL long borosilicate type 1 glass syringe with a 29-gauge, ½ inch stainless steel staked needle, a rigid needle shield, and a FluroTec™ coated butyl rubber stopper, preloaded into a commercially available fixed single dose, disposable, two step, mechanical autoinjector that administers a full dose of drug product into the subcutaneous tissue of the abdomen. It is intended for use by patients, caregivers, or a healthcare professional (HCP) at home or in a clinic setting.

4. SELECTION OF STUDY POPULATION

4.1. Inclusion Criteria

Female and male subjects are eligible for inclusion only if all the following criteria are met:

1. An Institutional Review Board (IRB) approved informed consent is signed and dated prior to any study-related activities.
2. Male and female subjects 45 to 80 years of age.
3. Has the ability to understand the requirements of the study and is willing to comply with all study procedures.
4. In the opinion of the Investigator, able to participate in the study.

4.2. Exclusion Criteria

A Subject is not eligible for inclusion if any of the following criteria apply:

1. Pregnant or lactating women or women of childbearing age who are not willing to use an adequate form of contraception.
2. Systolic BP (SBP) < 90 mmHg at screening or baseline.
3. Heart rate > 110 beats per minute (BPM) at screening or baseline.
4. Temperature > 38°C (oral or equivalent).
5. Serum potassium ≤ 3.0 or ≥ 5.5 mEq/L at screening.
6. Other significant cardiac abnormalities which may interfere with study participation or study assessments.
7. Current or planned treatment during the study with any IV therapies, including inotropic agents, vasopressors, levosimendan, nesiritide or analogues.
8. Presence of implanted ventricular assist device, cardiac defibrillator or pacemaker.
9. Severely impaired renal function, defined as an estimated glomerular filtration rate (eGFR) at screening admission < 30 mL/min/1.73 m², calculated using the simplified Modification of Diet in Renal Disease (sMDRD) equation.

10. Urinary retention due to bladder emptying disorders and/or urethral narrowing.
11. Presence or need for urinary catheterization.
12. Reported history of hepatic cirrhosis.
13. Administration of intravenous radiographic contrast agent within 72 hours prior to Screening.
14. Concomitant or any use within past 30 days of drugs known to interact with furosemide (aminoglycoside antibiotics, ethacrynic acid, high doses of salicylates, cisplatin, tubocurarine, succinylcholine, chloral hydrate, phenytoin, methotrexate, indomethacin or lithium).
15. Administration of an investigational drug or implantation of investigational device, or participation in another interventional clinical trial, within 30 days prior to Screening.
16. Any surgical or medical condition which in the opinion of the investigator may interfere with participation in the study or which may affect the outcome of the study.
17. Positive urine drug screen at Screening or Baseline.
18. Blood alcohol concentration \geq 2 mg/dL (0.02%) at Screening.
19. Alcohol breath test \geq 2 mg/dL (0.02%) on admission to the CRU.
20. History of severe allergic or hypersensitivity reactions to furosemide or any component of the SCP-111 formulation (tromethamine or benzyl alcohol).

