1.4. Risk Management

Subjects will be monitored in the Clinical Research Unit (CRU) for at least 12 hours after dosing with the study treatment and monitored. Subjects will be allowed liquid and solid oral intake ad libitum during the study with a minimum of 100 mL of fluid consumed for every 300 mL of urine output. Subjects with abnormal serum potassium levels at screening will be excluded from the study. Blood pressure and heart rate will be monitored during and after the injections.

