3. INVESTIGATIONAL PLAN

3.1. Overall Study Design and Plan

This is an open-label, single-center, single-dose, randomized, two-way (two-period) crossover study in healthy volunteers. Each Subject will complete Screening, Baseline, Treatment, and Follow-up Phases.

The Screening Phase will be conducted on an outpatient basis between 14 and 3 days prior to the Baseline visit. Subjects will be instructed to maintain a < 2-gram sodium diet and abstain from caffeine-containing products within 2 days prior to admission to the CRU. On arrival to the CRU (Day 0), baseline and final qualification assessments will be performed.

The Treatment Phase will be comprised of two crossover periods separated by a 3 ± 1 day washout period. During each CRU admission and through the washout period, Subjects will continue a < 2-gram sodium diet and abstain from caffeine-containing products. Subjects will be randomly assigned in a 1:1 ratio to 1 of 2 treatment sequences to receive IV furosemide and SC SCP-111 in the abdomen in Crossover Periods (ie, IV followed by SC or vice versa). Blood samples will be collected to measure plasma furosemide concentrations at pre-dose and for 12 hours post-dose. Prior to dosing in each Treatment Phase, subjects will void their bladder completely and urine will be collected starting after the injection through 12 hours post injection to determine total urine output and urinary sodium and potassium excretion. Assessment of injection site pain will be conducted for IV and SC administration using an 11-point pain scale. Photographs of the injection site will be performed prior to the IV and SC injection (baseline) and 4 hours post IV administration and 6 hours post SC administration. In addition, a photograph will be taken of the IV and SC injection site for any AE (i.e., erythema, edema, pruritus, bruising) that occurs at the site at the time of the event. Subjects will remain domiciled in the CRU for each Crossover Period during the Treatment Phase through 12 hours after administration of study drug. After final assessments are performed, Subjects may be discharged from the CRU if safety parameters are acceptable to the Investigator.

The Follow-up Phase will occur 24-48 hours (Day 5 ± 1) after discharge from the CRU following Crossover Period 2, completing Subjects' study participation.

[figure not shown]

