6.2.1. Study Phases

6.2.1.1. Screening (Day -14 through -3)

Subjects can be pre-screened ahead of enrollment by telephone and invited to the research center. Upon arrival to the research center, the study procedures will be explained. All Subjects who sign the informed consent form and satisfy the inclusion/exclusion criteria will be enrolled into the study.

The initial Screening visit will be conducted between 14 and 3 days prior to Baseline/CRU Admission on Day 0. The following procedures/assessments will be performed at Screening:

1. Informed consent (must be done prior to **any** of the following procedures, including asking subjects to discontinue prohibited medications)
2. Eligibility review
3. Medical history and demographics
 - Date of birth
 - Sex
 - Race
 - Ethnicity
 - Height (in)
 - Weight (lbs)
 - BMI (calculated from height and weight)
 - Medical History (self-reported; include onset dates)
 - Heart Failure
 - Hypertension
 - Stroke
 - Myocardial infarction
 - Unstable angina
 - Atrial fibrillation/flutter
 - Presence of implanted ventricular assist device, cardiac defibrillator, CardioMEMS™ or pacemaker

- Chronic obstructive pulmonary disease
 - Diabetes mellitus
 - Hepatic/liver disease
 - Chronic Kidney disease (If yes, stage)
 - Stage 1: Normal kidney function (GFR >90 mL/min/1.73 m² with urine findings, structural abnormalities, or genetic traits)
 - Stage 2: Mildly reduced kidney function (GFR (60-89 mL/min/1.73 m²))
 - Stage 3a: Moderately reduced kidney function (GFR (45-59 mL/min/1.73 m²))
 - Stage 3b: Moderately reduced kidney function (GFR 30-44 mL/min/1.73 m²)
 - Stage 4: Severe reduced kidney function (GFR 15-29 mL/min/1.73 m²)
 - Stage 5: Kidney failure (GFR < 15 mL/min/1.73 m² or dialysis)
 - Depression
 - Hyperlipidemia
 - Obstructive sleep apnea
 - Current Smoker (not current smoker if stopped smoking for at least 12 months)
4. Complete/full physical examination as described in Section 6.2.2.1
 5. Temperature
 6. Blood pressure
 7. Heart rate
 8. Screening labs will be performed to measure sodium, potassium, calcium, chloride, magnesium, carbon dioxide, blood urea nitrogen, serum creatinine, glucose, hemoglobin, hematocrit and blood alcohol.
 9. Urine drug screen
 10. Serum pregnancy test (for females of child-bearing potential)
 11. 12-Lead ECG as described in 6.2.2.2
 12. Prior medication assessment

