6.2.1.2. Baseline Assessment (Day 0)

Subjects will be admitted to the CRU on Day 0 (the day of study drug administration) for Baseline assessment and procedures. Low sodium diet (< 2 gram per day) and fluid intake ad libitum consisting of water, juice and caffeine free beverages are permitted while domiciled in the CRU. Subjects will be monitored during the study to ensure a minimum of 100 mL of fluid consumed for every 300 mL of urine output.

The following assessments will be completed at Baseline upon CRU admission:

1. Eligibility re-review
2. Limited physical examination as described in Section 6.2.2.1
3. Prior medication assessment
 - Time and date of last dose of oral loop diuretic (if receiving)
4. Weight measurement
5. Temperature
6. Blood pressure
7. Heart rate
8. Clinical laboratory tests as described in Section 6.2.2.3
9. Alcohol breath test
10. Urine drug screen
11. Urine pregnancy test as applicable
12. Randomization to treatment sequence
13. Photograph of Injection Site as described in Section 6.2.2.8

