6.2.1.5. Pre-Period 2 Assessment (Day 3 ± 1)

Subjects will present to the CRU on Day 3 ±1 for Pre-Period 2 assessment and procedures. Low sodium diet and fluid intake ad libitum consisting of water, juice and caffeine free beverages are permitted while domiciled in the CRU. Subjects will be monitored during the study to ensure a minimum of 100 mL of fluid consumed for every 300 mL of urine output.

The following assessments will be completed at the Pre-period 2 assessment upon CRU admission:

1. Limited physical examination as described in Section 6.2.2.1
2. Concomitant medication assessment

- a. Time and date of last dose of oral loop diuretic (if receiving)
3. Weight measurement
4. Temperature
5. Blood pressure
6. Heart rate
7. Clinical laboratory tests as described in Section 6.2.2.3
8. Alcohol breath test
9. Urine drug screen
10. Urine pregnancy test as applicable
11. Adverse events

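### Criterion 5 limits serum potassium at screening only; apply the same limits to the Day 0 and Pre-Period 2 results already scheduled before each dose

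*Protocol*

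**What the plan says.** Protocol Section 4.2, criterion 5 (same limits in the Synopsis): "Serum potassium ≤ 3.0 or ≥ 5.5 mEq/L at screening". Section 1.4 lists this kind of exclusion among the risk-management measures: "Subjects with abnormal serum potassium levels at screening will be excluded from the study".

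Two neighboring criteria also apply on the day of first dosing: "Systolic BP (SBP) < 90 mmHg at screening or baseline" and "Heart rate > 110 beats per minute (BPM) at screening or baseline". So does criterion 17, the urine drug screen.

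On timing, Section 6.2.1.1 states: "The initial Screening visit will be conducted between 14 and 3 days prior to Baseline/CRU Admission on Day 0". Section 3.1 adds: "The Treatment Phase will be comprised of two crossover periods separated by a 3 ± 1 day washout period". Section 6.2 puts the doses on Day 0 and Day 3 (± 1 day).

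Potassium is part of the pre-dose and post-dose chemistry panel (Section 6.2.2.3.2).
- **First dose.** Section 6.2.1.2 says "Subjects will be admitted to the CRU on Day 0 (the day of study drug administration) for Baseline assessment and procedures". Its list has an eligibility re-review as item 1, clinical laboratory tests as item 8 and randomization as item 12.
- **Second dose.** Section 6.2.1.5 says "The following assessments will be completed at the Pre-period 2 assessment upon CRU admission". Its list has clinical laboratory tests but no eligibility review.

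SAP Section 9.3.4.1 confirms that both samples come before treatment.

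**The concern.** The plan draws a potassium sample before each dose but does not say what result would stop the dose. The eligibility re-review on Day 0 cannot supply a limit, because criterion 5 refers to the screening sample and the re-review can only read that value again. At Pre-Period 2 there is no eligibility step at all.

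This matters for a named risk. Section 1.3 lists hypokalemia among the effects of furosemide, and Section 1.2 says subjects gain nothing beyond contributing to development. The second dose is the more exposed one: it follows 80 mg of a potassium-lowering drug by 2 to 4 days.

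Potassium can also move between screening and the first dose by a route the protocol permits. Section 5.8 lets users of oral furosemide, bumetanide or torsemide take part after a 24-hour hold. Section 6.2.1.5 asks for the last oral loop-diuretic dose, if any, so it foresees use during the washout.

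**Working it through.** The point concerns an eligibility limit and when it applies. It does not touch the sample size, power or alpha, and the plan states no figure to reproduce.

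**Age of the only limited value.** Inputs: screening 3 to 14 days before Day 0 (Section 6.2.1.1); second dose on Day 3 ± 1, that is Day 2 to Day 4 (Section 6.2).
- At dose 1: 3 to 14 days.
- At dose 2: 3 + 2 = 5 days to 14 + 4 = 18 days.

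**Possible oral loop-diuretic use after the screening sample.** The hold is 24 hours, so the time available before the first dose is 3 − 1 = 2 days to 14 − 1 = 13 days.

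**Scheduled potassium measurements and their limits.**

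| Measurement | Protocol section | Limit now | Limit after the change |
|---|---|---|---|
| Screening | 6.2.1.1 | yes | yes |
| Day 0, before dose 1 | 6.2.1.2 | no | yes |
| Hour 12, Period 1 | 6.2.1.3.3 | no | no |
| Pre-Period 2, before dose 2 | 6.2.1.5 | no | yes |
| Hour 12, Period 2 | 6.2.1.6.3 | no | no |

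Now 1 of 5; after the change 3 of 5, including both results that precede a dose. This counts rules, not risk.

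**What governs a low result on a dosing day.**
- Inclusion 4 and exclusion 16 rest on the investigator's opinion and have no screening restriction.
- Section 6.2.2.3.2 has the investigator judge whether an out-of-range value is clinically significant, and requires follow-up of those that are.
- Section 4.3 lets the investigator discontinue a subject at any time.

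None of these names a potassium value, and none requires the result to be seen before dosing. A result of 2.9 mEq/L would exclude a volunteer at screening, but on Day 0 or at Pre-Period 2 it triggers no written rule.

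**Feasibility of a check before dose 2.** Enrolling 21 to complete 18 leaves 21 − 18 = 3 spare. The documents give no removal rate, so I assume 2%, 5% or 10% of the 21 are lost to the check, independently and with no other dropout. The chance of at least 18 completers, P(X ≥ 18) for X ~ Binomial(21, 1 − s), is then:
- s = 2%: 0.999
- s = 5%: 0.981
- s = 10%: 0.848

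A Day 0 failure found before randomization costs a replacement volunteer and is not in this calculation.

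**The case against.** **A reader might infer that criterion 5 contradicts Section 1.4.** On timing it does not: Section 1.4 also says at screening. On level, the argument would be that 3.0 lies below normal, so some abnormal values stay eligible. The documents give no reference range, and criterion 5 can fairly be read as the definition of what Section 1.4 calls abnormal. If the laboratory's lower limit were 3.3, 3.4, 3.5 or 3.6 (assumed), the low but eligible values, to one decimal, would be 3.1 to 3.2, 3.1 to 3.3, 3.1 to 3.4 or 3.1 to 3.5. At 3.1 or below there would be none. Raising only the lower limit while leaving 5.5 alone is a threshold preference, not the repair of an error.

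**The comparison with blood pressure and heart rate is selective.** Those are bedside measures. Criteria 9 (eGFR) and 18 (blood alcohol) also rest on blood samples and also apply at screening only. Admission and dosing fall on the same day, which favors rapid checks. This explains the choice and stands as a practical constraint. But potassium is already drawn before both doses and bears directly on a named risk of the study drug.

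**Investigators would act on a low result.** They probably would. Discharge after the first period also depends on safety parameters acceptable to the investigator, with Hour 12 chemistry listed before it. A reader should not infer that subjects with low potassium will be dosed. The point is that no written rule prevents it.

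**A check at Pre-Period 2 could remove subjects according to their response to the first treatment.** This is fair. A subject who is not dosed leaves the Bioavailability Population, so the loss could be informative. It is a reason to keep the sponsor's own limits rather than a stricter one.

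**Conclusion.** The gap is in timing. Potassium has a numeric limit at screening and none at the two later measurements that precede a dose, so the only limited value is up to 14 days old at dose 1 and up to 18 days old at dose 2. That follows from the visit schedule and criterion 5 alone and needs no reference range.

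It is a safety gap covered at present only by discretion, and closing it is a cheap improvement. The bioequivalence analysis and its sample-size assumptions are unaffected. The number of subjects who would have a value outside 3.0 to 5.5 mEq/L on a dosing day cannot be computed from the documents. The completer probabilities rest on assumed removal rates.

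**What to change.** 1. **Criterion 5 (Synopsis and Section 4.2).** Keep both limits and add *or baseline* after *at screening*, matching the form of criteria 2 and 3.
2. **Section 6.2.1.2.** Require the Day 0 potassium result to be reviewed against these limits before randomization.
3. **Section 6.2.1.5.** Require the Pre-Period 2 result to be reviewed against the same limits before dosing. If it is outside them, hold the dose and give it only if a repeat within the Day 3 ± 1 window is within limits. State whether potassium replacement is allowed during a hold, because urinary potassium excretion is an endpoint.

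Moving the lower limit to the laboratory's lower limit of normal is optional. It needs a reference range that the documents do not give.

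**Cost.** Text edits and no new scheduled sample. The result must be available on the dosing day before dosing, and an occasional repeat sample may be needed. A second dose may be delayed by at most 4 − 2 = 2 days; a subject who arrives on Day 4 has only a same-day repeat. A subject whose second dose is withheld leaves the Bioavailability Population, against 3 spare subjects. Planned sample size, endpoints and analysis methods stay as they are.

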eGFR	Estimated Glomerular Filtration Rate
EP	European Pharmacopoeia
F	Fahrenheit
FDA	Food and Drug Administration
GCP	Good Clinical Practice
HCP	Healthcare Professional
ICH	International Conference on Harmonization
IFU	Instructions for Use
IM	Intramuscular
IN	Inches
IND	Investigational New Drug
IP	Investigational Product
IRB/EC	Institutional Review Board/Ethics Committee
IV	Intravenous
lbs	Pounds
Mg/dL	Milligrams per Deciliter
Min	Minute
mL	Milliliter
mmHg	Millimeters of mercury
mEq/L	Milliequivalent per Liter
OTC	Over-The-Counter
PD	Pharmacodynamics
PK	Pharmacokinetics

SAE	Serious Adverse Event
SBP	Systolic Blood Pressure
SC	Subcutaneous
sMDRD	Simplified Modification of Diet in Renal Disease
USP	United States Pharmacopeia
V	Systemic Volume
V_z/F	Apparent Systemic Volume of Distribution

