6.2.2.9. Alcohol and Caffeine

Subjects will abstain from alcohol and caffeine-containing products (including decaffeinated coffee), from 2 days prior to the Baseline visit, during both Crossover Periods and the washout period and until completion of procedures in Crossover Period 2. Subjects will undergo an alcohol breath test at each CRU admission.

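### Exclusion criteria 18 and 19 equate 2 mg/dL of alcohol with 0.02%, but the two figures differ tenfold, so a reading between them is both excluded and allowed.

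*Protocol*

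**What the plan says.** Protocol Section 4.2 has two alcohol exclusions. Criterion 18 excludes a subject whose blood alcohol concentration is at or above "2 mg/dL (0.02%) at Screening". Criterion 19 excludes a subject whose alcohol breath test is at or above "2 mg/dL (0.02%) on admission to the CRU". The Synopsis repeats both with the same figures.

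The protocol's abbreviation list expands the unit as "Milligrams per Deciliter". Neither the protocol nor the SAP says what kind of percent is meant, which figure takes priority, or in what unit the laboratory or the breath device reports.

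The criteria are decisive one at a time: "A Subject is not eligible for inclusion if any of the following criteria apply". Blood alcohol is one of the screening laboratory tests (Sections 6.2.1.1 and 6.2.2.3.1). The breath test is done at Baseline (Section 6.2.1.2) and again before Period 2 (Section 6.2.1.5). Section 6.2.2.9 confirms the repetition: "Subjects will undergo an alcohol breath test at each CRU admission". No separate threshold is given for the second admission.

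**The concern.** Each criterion states its threshold twice, once in mg/dL and once in parentheses as a percent, as if the second were a conversion of the first. On the usual reading of blood alcohol percent the conversion is wrong by a factor of ten. A reader who works in mg/dL and one who works in percent would then apply different rules while both follow the protocol.

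What is at stake is eligibility and its records. A subject with a reading between the two figures could be recorded as a screen failure, as a valid enrolment or as an eligibility deviation, depending on which figure was used. Deviations must be documented (Protocol Section 9.1.8). The SAP lists screening failures with reasons (Section 9.3.5.1) and lists protocol deviations (Section 9.3.5.4), so the ambiguity would carry into the study report.

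**Working it through.** **Inputs**

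- Threshold in mg/dL: 2 (Protocol Section 4.2, criteria 18 and 19; same in the Synopsis).
- Threshold in percent: 0.02% (same places).
- Unit: milligrams per deciliter, with 1 dL = 100 mL (Protocol abbreviation list).
- Assumption: percent means weight per volume, that is, grams per 100 mL. The documents do not define it, so other conventions are tried below.
- Assumption: the breath result is expressed as a blood-equivalent concentration, because criterion 19 uses the same units as criterion 18.

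**Attempt to reproduce the plan's equivalence**

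Percent (w/v) = g per 100 mL = (mg/dL) / 1000.

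- From mg/dL to percent: 2 / 1000 = 0.002%. The protocol says 0.02%, so the figure is not reproduced.
- From percent to mg/dL: 0.02 × 1000 = 20 mg/dL. The protocol says 2 mg/dL.
- Ratio: 20 / 2 = 10.

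**Other conventions**

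The densities here are assumptions that do not come from the documents: 1.04 to 1.06 g/mL for blood (1.055 used in the table) and 0.789 g/mL for ethanol.

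| Reading of the percent | 2 mg/dL equals | 0.02% equals | Ratio to 2 mg/dL |
|---|---|---|---|
| Weight/volume | 0.002% | 20 mg/dL | 10 |
| Weight/weight | 0.002 / 1.055 = 0.0019% | 20 × 1.055 = 21.1 mg/dL | 10.6 |
| Volume/volume | 0.002 / 0.789 = 0.0025% | 20 × 0.789 = 15.8 mg/dL | 7.9 |

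None of the three turns 2 mg/dL into 0.02%. The number 0.02 does match 2 mg/dL as per mille (2 mg/dL = 20 mg/L = 0.02 g/L), but the protocol prints a percent sign.

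**Consequence for classification (weight/volume)**

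| Reading, mg/dL | Excluded at ≥ 2 mg/dL | Excluded at ≥ 0.02% (20 mg/dL) |
|---|---|---|
| 1 | no | no |
| 2 | yes | no |
| 10 | yes | no |
| 19.9 | yes | no |
| 20 | yes | yes |
| 25 | yes | yes |

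The two figures agree below 2 mg/dL and from 20 mg/dL upward. They disagree on every reading from 2 to below 20 mg/dL.

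**The case against.** The mismatch itself is hard to defend. It appears in two criteria, each in two places, so a stray character in the file is not a credible explanation. The case on the other side concerns how much it matters.

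- **Reporting units are unknown.** The documents give none for the laboratory or the breath device. A picture in which one works in mg/dL and the other in percent is an illustration. This stands, but each criterion already contradicts itself whatever the units.
- **One site, two separate tests.** Blood is tested only at Screening and breath only at admission. If each test is read in a single unit, all subjects face the same cut-off for that test. The likelier failure is then one uniform but unintended threshold, or different thresholds at the two visits, and not subject-to-subject inconsistency. This is fair and narrows the practical risk.
- **Abstinence empties the band at admission.** Section 6.2.2.9 requires no alcohol from 2 days before Baseline to the end of Crossover Period 2, so a compliant subject should read near zero at each breath test. This stands for criterion 19. It does not help criterion 18, because Screening runs from Day -14 to Day -3, before the abstinence window opens.
- **No route to the primary result.** The threshold plays no part in the AUC endpoints, the sample size, the analysis populations or the ANOVA, and in a crossover an eligibility ambiguity does not favour either treatment. This stands.
- **Investigator discretion.** Inclusion 4 and exclusion 16 let the investigator keep out a doubtful subject. They cannot admit a subject whom criterion 18 or 19 excludes, so they do not resolve the conflict.

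These points limit the impact. None of them makes the two figures agree or tells the site which one to use.

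**Conclusion.** The concern holds. Criteria 18 and 19 are wrong as written, in both Section 4.2 and the Synopsis. The factor is exactly 10 if percent means grams per 100 mL, and about 8 to 10.6 under the other conventions with the assumed densities. Readings from 2 to below 20 mg/dL (0.002% to below 0.02%) are classified in opposite ways.

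The documents do not say how many of the planned 21 subjects, or of those screened, would give such a reading. The number may well be small, and the exposure is greater at Screening than at admission. The SAP's precedence over the protocol (SAP Section 9) does not settle the matter, because the SAP states no alcohol limit. The point should be corrected because it is a binding eligibility rule. It does not threaten the bioavailability conclusion.

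**What to change.** The sponsor should decide which threshold was intended and restate criteria 18 and 19 with one numerically consistent figure, in Section 4.2 and the Synopsis together. For each test, the text should name the unit that the laboratory or breath device reports. If a second unit is kept in parentheses, it should be a correct conversion, with the kind of percent stated. The sponsor should also say whether the same threshold applies to the breath test before Period 2, where none is given.

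The cost is a short protocol correction, with the eCRF edit check and any laboratory or device limit set to match. If subjects have already been screened, their alcohol readings should be checked for values from 2 to below 20 mg/dL, so that any affected eligibility decision can be documented. No statistical analysis changes.
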